## 2 BACKGROUND

The TRIUMPH study, or trans Research-Informed communities United in the Mobilization for the Prevention of HIV, is a new study responding to a pressing need for culturally-relevant community-led pre-exposure prophylaxis (PrEP) programs for transgender communities, especially for trans women of color who are most affected by the HIV epidemic. The TRIUMPH study will strive to identify the most effective PrEP service provision strategies which take into account the particular facilitators and barriers that transgender communities encounter in the health care system. To date, transgender women included in HIV prevention studies have been lumped into the larger aggregate of Men who have sex with Men (MSM) without taking into account the unique sociocultural context of transgender women. The TRIUMPH study will also include transgender men and other members of various transgender communities. The TRIUMPH project's goal is to identify the best methods to deliver PrEP safely and effectively to transgender communities while achieving the highest levels of adherence possible.

PrEP is the newest and most promising biomedical HIV prevention intervention yet developed and tested. The first clinical trial of PrEP ('iPrEx' or iniciativa Profilaxis Pre-Exposición) included MSM and transgender women who were at higher risk for HIV infection, and found that daily oral Truvada PrEP reduced the risk of HIV acquisition by 44% on an intention to treat basis [1]. However, a sub-analysis of the iPrEx data conducted by Deutsch *et al*, found zero effectiveness on an intention to treat basis among the small subgroup of transwomen in the study [2]. Further analyses revealed that the subgroup of trans women in iPrEx who were using hormones were less likely to have protective drug levels than those trans women not on hormones (OR 0.14,  $p < 0.001$ ). It is unclear if this difference is behavioral (less drug uptake) or biomedical (drug-drug interactions) in nature, or due to some combination of these factors, given the lack of pharmacokinetic (PK) studies testing for interactions between cross-sex hormone therapy (HT) and TDF/FTC, the active ingredients of Truvada. While there are studies of systemic drug-drug interactions between oral contraceptives and TDF, no such studies have been done with FTC, and no studies have been done with gender affirming HT, which differs from hormonal contraception in several respects. Drug-drug interactions with bioidentical 17-beta estradiol used for gender affirming hormone therapy among transgender women have not been studied.

The Interactions BETWEEN Antiretrovirals And Transgender Hormones, or I-BrEATHe study, described in this protocol is a sub study of the TRIUMPH study. I-BrEATHe will address one of the secondary aims of the TRIUMPH study which is to assess the pharmacokinetic drug-drug interactions between cross-sex HT and daily oral FTC/TDF.

Given that there are no PrEP studies to date that have specifically enrolled trans identified men, or have looked at the interactions between masculinizing HT and FTC/TDF, I-BrEATHe will enroll both transgender women and men. Transgender men report sexual rapports without condoms both vaginally and anally (range 26-60%), exhibit patterns of STIs transmission and unwanted pregnancies. Transgender men also report use of sex for gender affirmation. Small convenience samples show that HIV prevalence is between 2-5% [3, 4]. To date, there are no programs or PrEP recommendations specific for transgender men.

## 2.1 Overview of Non-Clinical Studies

N/A

## 2.2 Overview of Clinical Studies

There have been a large number of trials conducted with Truvada PrEP, including several demonstration projects. While there is no evidence to suggest that TDF/FTC interacts with commonly used feminizing or masculinizing hormone regimens, and evidence from studies of ARV interactions with hormonal contraceptives have been reassuring, no direct study of these interactions has been conducted to date.

Our team led the only trans-specific sub analysis to date of the iPrEx randomized controlled trial (RCT) data as well as the open label extension (OLE) study, which included periodic dried blood spot (DBS) drug level monitoring [2]. In iPrEx, gender identity data was not collected using current best practices (“two-step” method [5]), making the identification of transgender participants in this multinational, multicultural and multilingual trial difficult. As all iPrEx participants had been assigned male sex at birth, a transgender subgroup of 339/2499 participants (14% of overall sample) was constructed comprised of the 29 (1%) who identified as women, 296 (12%) who identified as “trans”, and 14 (1%) who reported use of feminizing hormones. None had undergone gender affirming genital surgery. Compared with MSM, transgender women more frequently reported transactional sex, receptive anal intercourse without a condom, or more than 5 partners in the past 3 months. Excluding those with a male identity who also used feminizing hormones, trans- and woman-identified participants were less likely to have TDF levels detected on random testing in the RCT (OR=0.39, 95% CI = 0.16 to 0.96, p=0.04). While there was no effectiveness of PrEP for transgender women on an intention-to-treat basis, none of the transgender participants who seroconverted had detectible drug levels at the time of HIV diagnosis. In comparison to MSM in the OLE, transgender participants had less time with protective drug concentrations (17% vs 35%, p<0.001) and were less likely to have concentrations indicating > 3 tablets/week (OR 0.71, 95% CI 0.49 to 1.03, p=0.07). Of the two transgender women who seroconverted during the OLE, both had drug levels below 350 fmol/punch in DBS, the level associated use of 2 tablets per week at the time of seroconversion. The lower concentrations were more likely if the transgender women used feminizing hormones.

Of the 7 clinical trials of Truvada PrEP for HIV prevention conducted to date, iPrEx is the only one with confirmed enrollment of trans women [6]. No clinical studies or demonstration projects were conducted with transgender men.

For more detail regarding PrEP clinical trials, please refer to the Prescribing information for Truvada.

## 3 STUDY RATIONALE

The fact that concentrations of FTC/TDF were especially low among transgender women reporting use of feminizing hormones in the iPrEx study, which may reflect less PrEP use or a drug-drug interaction, is of high interest given that concerns about the impact of PrEP

on gender affirming hormone therapy is the main barrier for uptake of PrEP among transgender women [7]. While transgender men as a group have also been shown to be at elevated risk for HIV infection [4, 8], no information about PrEP use and drug levels is available for transgender men since they have never been formally included in PrEP research. Therefore, there are no data on the potential effects of testosterone on FTC/TDF drug concentrations. FTC/TDF drug concentrations have emerged as strong correlates of protection in PrEP trials, accounting for the majority of the variation in PrEP benefits across trials and across individual participants in trials. For example, while oral FTC/TDF PrEP had 44% efficacy on an intention to treat basis in iPrEx, the protective effect was more than 90% among those with detectable drug and negligible among those with no detectable drug in blood [1, 9].

The pharmacokinetic study of PrEP metabolites concentrations in association with feminizing and masculinizing hormones using directly observed therapy (DOT) will allow to establish whether interactions exist between these drugs. I-BrEATHe also provides an opportunity to include transgender men in PrEP research. Though transgender men are likely to be at lower risk for HIV acquisition than transgender women, the lack of available data regarding use of PrEP in transgender men must be remediated. I-BrEATHe will recruit equal numbers of transgender women who are using estradiol plus spironolactone (the most common HT regimen) and transgender men who are using testosterone. The primary aim will be to measure the intracellular active metabolites of TDF/FTC, tenofovir diphosphate (TFV-DP) and emtricitabine triphosphate (FTC-TP), levels in DBS collected after 1, 2, 3, and 4 weeks of video-observed Truvada for PrEP daily dosing, and comparing drug levels in the two groups receiving HT to previously acquired DBS drug levels data in MSM [9-11].

### 3.1 Risk / Benefit Assessment

Oral Truvada for PrEP has been FDA approved since 2012. At this time, there is plentiful evidence to support the use of daily oral FTC/TDF in HIV-1-uninfected heterosexual biological men and women, and men who have sex with men for HIV prevention [12]. The toxicity and tolerability of daily oral FTC/TDF in HIV-uninfected individuals have been established. Side effects that may arise in the first weeks of PrEP use -- nausea, abdominal cramping, vomiting, dizziness, headache, and fatigue usually go away without treatment interruption (see Truvada Prescribing information for more details). Known potential risks can be effectively managed by experienced PrEP providers. Participants enrolled in this study will be provided Truvada for PrEP within the confines of an established PrEP clinic, and will benefit from the expertise of trained staff. Individuals who may be susceptible to the possible nephrotoxic effect of FTC/TDF as determined by the measure of creatinine clearance (see exclusion criteria) will not be enrolled in the study. Long term effect of Truvada use (such as bone density loss or kidney dysfunction) are unlikely to occur over the course of this short study in otherwise healthy participants [13-15]. Participants will be seen weekly by a clinician, and any adverse event immediately addressed, in addition participants will be interacting daily with study staff via phone, providing an opportunity to address any questions or concerns. Moreover, the daily interactions with study staff will provide support for adherence. Concerns about risks of combining gender-affirming hormone therapy and PrEP will be alleviated by trained providers with expertise in the management of both antiretroviral and hormone

therapy. Guidelines for these matters will be provided by the UCSF Center of Excellence for Transgender Health (CoE-T).

## **4 STUDY OBJECTIVES**

### **4.1 Primary Objective**

To assess pharmacokinetics for daily oral FTC/TDF in transgender women and transgender men, and to determine if FTC/TDF drug concentrations are lower among transgender women who are using hormone therapy and in transgender men who use testosterone compared to historical controls in non-transgender MSM.

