## PROTOCOL SYNOPSIS

TITLE	I-BrEATHe - Interactions BEtween Antiretrovirals And Transgender Hormones.
SPONSOR	[name] and [name]
FUNDING ORGANIZATION	University of California Office of the President via the California HIV/AIDS Research Program
NUMBER OF SITES	1
RATIONALE	
Drug concentrations after receipt of oral Truvada Pre Exposure Prophylaxis (or PrEP) appeared to be lower in transgender women compared to Men who Have Sex with Men (MSM) in the iPrEx study. Reasons for the lower drug concentrations may be behavioral or biomedical, or a combination of both. There are few to no studies which investigate the potential drug to drug interactions between the components of Truvada (emtricitabine or FTC and tenofovir disoproxil fumarate or TDF) and feminizing hormones. In addition, no PrEP studies have ever included transgender men; therefore no knowledge exists on the potential interactions between FTC/TDF and masculinizing hormones.
 
The pharmacokinetic study, using directly observed therapy (DOT), is designed to address the question whether feminizing or masculinizing hormones affect FTC/TDF levels in transgender women or transgender men respectively.

STUDY DESIGN	This is a pharmacokinetic study
PRIMARY OBJECTIVE	Assess pharmacokinetic drug-drug interactions between tenofovir disoproxil fumarate/emtricitabine (TDF/FTC) and cross-sex hormone therapy.
SECONDARY OBJECTIVES	Assess Adverse Events related to TDF/FTC in transgender men and women and compare to historical controls in non transgender MSM
NUMBER OF PARTICIPANTS	48 (24 transgender women and 24 transgender men)
PARTICIPANT SELECTION CRITERIA	
Inclusion Criteria:
 
All subjects:
 
 
• HIV antibody seronegative (negative HIV rapid test),
 
• 18 years or older,
 
• Has a smart phone with access to two-way video call capability,
 
• Willingness to be contacted for a short call every day for 4 weeks,
 

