### 7.2 Inclusion Criteria:

All subjects:

- HIV antibody seronegative (negative HIV rapid test),
- 18 years or older,
- Has a smart phone with access to two-way video call capability,
- Willingness to be contacted for a short call every day for 4 weeks,
- Adequate renal function (creatinine clearance  $\geq 60$  ml/min estimated by the Cockcroft Creatinine Clearance Formula),

- Provides written informed consent,

For Transgender women:

- Male assigned sex at birth, and self-reported current gender identity as “woman” or “transgender women”, or other trans-feminine spectrum identity,
- Current feminizing Hormone Therapy (HT) use for at least 6 months,

For Transgender men:

- Female assigned sex at birth, and self-reported current gender identity as “man” or “transgender man”, or other trans-masculine spectrum identity,
- Current masculinizing Hormone Therapy (HT) use for at least 6 months with testosterone

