#### 10.3.2 Hormonal Therapy Profile

Blood will be drawn at enrolment and at study exit for quantification of estradiol, and total and free testosterone levels, as well as sex hormone binding globulin (SHBG) and dihydrotestosterone (DHT) using Liquid Chromatography-Tandem Mass Spectrometry (LC/MS/MS) and/or equilibrium dialysis. These measures will be used for the outcome analyses.

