### **15.3 Analysis of Primary Endpoint**

We will compare levels of TFV-DP in dried blood spots and rates of adverse events between trans men and trans women and a group of MSM historical controls from the iPrEx OLE study. We will compare log transformed TFV-DP levels using a linear mixed effects model with factors for group (trans men v. trans women v. MSM) and times (1, 2, 3 and 4 weeks after initiation) and their interaction with an unstructured covariance across visits and test for differences at between groups at each time point. If values appear to violate the normal distribution, we will obtain p-values and confidence intervals using the bootstrap. All p-values will be two-sided with p-value < 0.05 considered statistically significant. Adverse events will be compared using the Fisher exact test.

Adverse event rates will be coded by body system and MedDra classification term. Adverse events will be tabulated and will include the number of patients for whom the event occurred, the rate of occurrence, and the severity and relationship to study drug.

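### Trans men v. MSM cannot separate testosterone from sex assigned at birth, so the synopsis and section 3 claim an answer on masculinizing hormones that the design cannot give

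*Combined protocol and SAP*

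**What the plan says.** **The question claimed.** The synopsis rationale says the study will address "whether feminizing or masculinizing hormones affect FTC/TDF levels in transgender women or transgender men respectively". The synopsis primary objective is to assess drug-drug interactions between TDF/FTC and cross-sex hormone therapy. Section 3 says the pharmacokinetic study under DOT "will allow to establish whether interactions exist between these drugs".

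**The comparison planned.** Section 3 describes the primary aim as measuring the metabolites in DBS and "comparing drug levels in the two groups receiving HT to previously acquired DBS drug levels data in MSM". Section 4.1 asks whether concentrations are lower in trans women on hormone therapy and "in transgender men who use testosterone compared to historical controls in non-transgender MSM". The model in section 15.3 contains group (three levels), week and their interaction, with iPrEx OLE as the source of controls. It names no hormone, weight or renal-function term.

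**Who is in each group.** Section 7.2 admits trans men by "Female assigned sex at birth, and self-reported current gender identity as" man, transgender man or another trans-masculine identity, with at least 6 months of testosterone. Section 2.2 reports that everyone in iPrEx was assigned male at birth. Section 7.3 excludes anyone who expects to change hormone therapy during the study, and section 14 makes such a change a protocol violation.

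**Hormone measurements.** Section 10.3.2 takes estradiol, total and free testosterone, SHBG and DHT at enrolment and exit, and says: "These measures will be used for the outcome analyses". Section 15 does not say how.

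**The concern.** A drug-interaction claim needs a contrast in which hormone exposure varies while birth sex does not, or in which the two can be separated. For trans men there is none. A difference from MSM, or the lack of one, mixes any testosterone effect with whatever differs by birth sex, such as body size or renal clearance, and with the change of study. The two parts may add or cancel.

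What is at stake is the conclusion for half the participants. A result of no lower than MSM could be reported as testosterone not interacting with FTC/TDF, and a lower result could be reported as an interaction. Neither would follow. Section 3 itself says that no data exist on testosterone and these drug concentrations, so such a statement would have nothing to correct it.

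**Working it through.** **1. The plan's own figures.** Section 15.4 gives 0.52 log as 1.68-fold and 0.70 log as 2.0-fold. Check: exp(0.52) = 1.68 and exp(0.70) = 2.01, so natural logs are used. The 81% and 80% power cannot be reproduced because neither the SD nor the number of MSM controls is stated. The point below does not depend on them.

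**2. What the three groups can estimate.** Coding from sections 2.2, 7.2 and 15.3, with MSM controls taken as unexposed to cross-sex hormones:

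| Group | Assigned female (F) | Feminizing HT (H) | Testosterone (T) | Current study (S) |
|---|---|---|---|---|
| MSM | 0 | 0 | 0 | 0 |
| Trans women | 0 | 1 | 0 | 1 |
| Trans men | 1 | 0 | 1 | 1 |

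At any week the group contrasts are:

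- Trans women − MSM = H + S
- Trans men − MSM = F + T + S
- Trans men − trans women = F + T − H

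F and T appear only as a sum. With the intercept there are five parameters and the matrix has rank 3. If the historical-control effect S is assumed to be zero, the rank is 3 for four parameters: H becomes estimable from trans women v. MSM, but T still does not. So this is a problem for trans men beyond the general weakness of historical controls. Because hormone therapy may not change on study, there is no off-testosterone period within a person either.

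Adding a row for people assigned female, off testosterone and studied concurrently (1, 0, 0, 1) would give T as trans men minus that group. A historical group of that kind would do so only if S = 0.

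**3. Illustrative size.** The documents give no birth-sex effect. Assume that concentration scales as weight or clearance to the power −k, with k from 0.5 to 1, and that trans men average 10% to 20% lower than MSM. Then shift = −k × ln(ratio):

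- k = 0.5, ratio 0.90: 0.5 × 0.105 = 0.053 log
- k = 1, ratio 0.80: 1 × 0.223 = 0.223 log

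A shift of that size would offset a testosterone-driven fall of 1 − exp(−0.053) = 5% to 1 − exp(−0.223) = 20%. Against the 0.70 log in section 15.4 it is 0.053/0.70 = 8% to 0.223/0.70 = 32%. A true 0.70 log fall would appear as 0.65 to 0.48 log. Both inputs are assumptions, and the direction could be the reverse.

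**4. What a within-group slope could show.** For 24 trans men, the correlation detectable with 80% power at two-sided 0.05 by Fisher's z is tanh[(1.96 + 0.84)/√(24 − 3)] = tanh(0.61) = about 0.55. Only a strong association would be found reliably, and all 24 are on testosterone, so treated is never compared with untreated.

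**The case against.** The strongest reply is that section 4.1 names no testosterone effect. It asks whether concentrations are lower than in MSM, and the contrast can answer that. This stands. A reader might infer that the primary objective as worded in section 4.1 cannot be met; the text does not support that. The problem lies in the synopsis and section 3, and in reading the result through them.

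MSM are also a defensible benchmark. Section 3 ties drug concentration to protection and says that no drug-level data exist for trans men, so whether they reach MSM exposure is worth knowing. This stands too, and it is the reason to keep the contrast and relabel it.

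Section 15.4 limits its sufficiency claim to feminizing hormones. That is correct, but the synopsis and section 3 carry no such limit.

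Section 15.3 also permits trans men v. trans women, so MSM are not the only possible comparator. As shown, that contrast does not help.

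Section 15 promises a detailed SAP before the final analysis, which could define the hormone-level analysis. It could, but a SAP cannot make the testosterone effect identifiable from these groups.

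Finally, the illustrative shift would shrink a two-fold fall but not cancel it. Under those assumptions that is right. They are not bounds, however, and the non-identifiability holds whatever the size.

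**Conclusion.** The point holds for the interpretation claimed, not for the comparison itself. The synopsis and section 3 say the study will determine whether masculinizing hormones affect FTC/TDF levels; with these three groups the testosterone effect is not identifiable. This follows from the eligibility criteria and the choice of controls. It needs no numerical assumption, only that MSM controls count as unexposed.

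The size and direction of the resulting bias are unknown. The 0.05 to 0.22 log shift is an illustration from assumed inputs, and the documents do not support expressing it in standard errors, since they give neither an SD nor a control sample size.

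Two stronger readings are tempting and should be resisted. One is that adjusting for weight and clearance would recover the testosterone effect. The documents do not show that these data exist for the MSM controls, adjustment cannot remove everything tied to birth sex, and after at least 6 months of testosterone both variables may themselves have been altered by it. The other is that a hormone-level slope within trans men could serve as the evidence on interaction. With 24 people and no unexposed group it cannot, and a null slope would invite the same false reassurance.

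**What to change.** 1. **Synopsis (rationale and primary objective) and section 3.** For trans men, state that the study compares drug exposure on testosterone with an MSM benchmark. Bring the synopsis objective into line with section 4.1, which is already descriptive.
2. **Section 15.3, interpretation.** Add a sentence such as: *Trans men v. MSM compares exposure; because testosterone use and sex assigned at birth coincide, neither a difference nor its absence will be attributed to testosterone.* Say the same of trans men v. trans women.
3. **Section 15.3, exploratory analysis.** Specify what section 10.3.2 commits to: week-4 log TFV-DP regressed on testosterone within trans men, and on estradiol within trans women, reporting the slope and 95% CI, with and without weight and creatinine clearance. Name in advance which hormone measure and visit are used. Label it supportive only, and state its limits: no unexposed group, low precision with 24 per group, hormone sampling not timed to the hormone dose, and weight and clearance possibly affected by testosterone.
4. **Adjusted MSM contrast.** Include a weight- and clearance-adjusted version only as a sensitivity analysis, and only if those data are available for the controls.

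The cost is wording and a small set of regressions on study data already scheduled for collection (hormone levels in section 10.3.2, weight in 10.1.5, creatinine clearance in 10.2.1), with no new participants, visits or assays. The downside is a weaker claim for trans men and a slope that will probably be imprecise.
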